Severe infusion reactions have been reported in less than 1.0% of patients in clinical trials of nivolumab. Discontinue nivolumab in patients with severe or life-threatening infusion reactions. Interrupt or slow the rate of infusion in patients with mild or moderate infusion reactions.

1.5.1.6.15 3.6.10 Embryo-Fetal Toxicity

Based on its mechanism of action and data from animal studies, nivolumab can cause fetal harm when administered to a pregnant woman. In animal reproduction studies, administration of nivolumab to cynomolgus monkeys from the onset of organogenesis through delivery resulted in increased abortion and premature infant death. Advise pregnant women of the potential risk to a fetus. Advise females of reproductive potential to use effective contraception during treatment with a nivolumab-containing regimen and for at least 5 months after the last dose of nivolumab

1.5.1.6.16 3.6.11 Drug Related Deaths

Based on reports from the safety data base the rate of death on treatment or within 30 days of the last dose of study drug was 4.7%. Serious adverse reactions occurred in 47% of patients receiving nivolumab. The most frequent serious adverse reactions reported in at least 2% of patients were acute kidney injury, pleural effusion, pneumonia, diarrhea, and hypercalcemia.

The most common adverse reactions (reported in at least 20% of patients) were asthenic conditions, cough, nausea, rash, dyspnea, diarrhea, constipation, decreased appetite, back pain, and arthralgia.

1.6 4.0 Summary of investigational program [Atezolizumab]

Atezolizumab is a programmed death-ligand 1 (PD-L1) blocking antibody indicated for the treatment of patients with locally advanced or metastatic urothelial carcinoma. Atezolizumab is an Fc-engineered, humanized, monoclonal antibody that binds to PD-L1 and blocks interactions with the PD-1 and B7.1 receptors. Atezolizumab is a non-glycosylated IgG1 kappa immunoglobulin that has a calculated molecular mass of 145 kDa.

Atezolizumab injection for intravenous infusion is a sterile, preservative-free, and colorless to slightly yellow solution in single-dose vials. Each mL of Atezolizumab contains 60 mg of atezolizumab and is formulated in glacial acetic acid (16.5 mg), L-histidine (62 mg), sucrose (821.6 mg), polysorbate 20 (8 mg), pH 5.8.

1.6.1.1 4.1 Clinical Pharmacology

1.6.1.1.1 4.1.1 Mechanism of Action

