4.5.7 Embryo-Fetal Toxicity

Based on its mechanism of action, Atezolizumab can cause fetal harm when administered to a pregnant woman. Animal studies have demonstrated that inhibition of the PD-L1/PD-1 pathway can lead to increased risk of immune-related rejection of the developing fetus resulting in fetal death. If this drug is used during pregnancy, or if the patient becomes pregnant while taking this drug, advise the patient of the potential risk to a fetus. Advise females of reproductive potential to use effective contraception during treatment with Atezolizumab and for at least 5 months after the last dose.

1.6.1.5.7 4.5.8 Drug related deaths

No information currently available.

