The main immunological end-point will be the induction or boosting of treatment induced T cells (CD4+ and CD8+) and B cells for defined antigen approaches. In addition, the magnitude and duration of T and B cell responses will be examined. Treatment-induced responses will be calculated as the difference between the pre-treatment measurement and the measurement at the different time points at which blood was collected (time of evaluation) in the same patient. The percentage of patients with the induction of treatment-induced T and B cell responses will be reported.

1.11 8.0 Subject Selection Criteria

1.11.1.1 8.1 Inclusion Criteria

1. Ability to understand and the willingness to sign a written informed consent document;
2. Any prior therapy is permitted except prior therapy with PD1/PDL1 inhibitor.
3. Histologic diagnosis of metastatic renal cell carcinoma or urothelial cancer;
4. Patients must have at least 2 distinct measurable metastatic sites at least 1 cm or larger in their largest diameter per RECIST 1.1
5. Patients must have adequate organ and marrow function as defined by initial laboratory tests:
 - WBC $\geq 2000/uL$
 - ANC $\geq 1000/uL$
 - Platelets $\geq 50 \times 10^3/uL$
 - Hemoglobin $\geq 10.0 \text{ g/dL}$
 - Creatinine $\leq 3.0 \times \text{ULN}$
 - AST/ALT $\leq 2.5 \times \text{ULN}$
 - Bilirubin $\leq 3.0 \times \text{ULN}$, (except patients with Gilbert's Syndrome, who must have a total bilirubin less than 3.0 mg/dL);
6. At least 2 weeks since last chemotherapy and 4 weeks since last immunotherapy treatment.
7. At least 2 weeks since last radiation therapy.
8. Performance status ECOG 0-1
9. Men and women, ages > 18 years of age.
10. Life expectancy > 3 months
11. Stable brain metastases for at least 4 weeks and not steroid dependent
12. Women of childbearing potential (WOCBP) must be using an adequate method of contraception to avoid pregnancy throughout the study and for up to 8 weeks after the study in such a manner that the risk of pregnancy is minimized. Should a woman become pregnant or suspect she is pregnant while she is enrolled in this study, she should inform her treating physician immediately.

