10. Women who:
 - a) are unwilling or unable to use an acceptable method to avoid pregnancy for the entire study period and for at least 8 weeks after cessation of study drug, or
 - b) have a positive pregnancy test at baseline, or
 - c) are pregnant or breastfeeding
11. Prisoners or subjects who are compulsorily detained (involuntarily incarcerated) for treatment of either a psychiatric or physical (e.g., infectious) illness

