15.0 Study Procedures and Observations - Nivolumab Alone and Nivolumab plus Radiation

Procedure	Screening Visit (- 28 days)	Day 1 ^h	Day 3 ^h	Day 5 ^h	Day 15 ^h	Day 29 ^h	Day 43 ^h	Day 57 ^h	Day 63 (+/-7 days)	F/UQ 9wks (±7days) for first year ^k	Follow up Q12 weeks (±7days) after 1 st year ^k years 2 and 3
Informed Consent	X										
Inclusion/Exclusion Criteria	X										
Medical History	X										
Pregnancy Test	X	X ^a				X ^a	X ^a	X ^a	X ^a		
Physical Examination Complete	X										
Physical Examination Limited		X				X	X	X	X	X	X
Vital Signs	X	X				X	X	X	X	X	X
Adverse Events Assessment	X	X				X	X	X	X	X	X
Serum Chemistry ^b	X	X				X	X	X	X	X	X
Hematology ^b	X	X				X	X	X	X	X	X
Urinalysis	X	X				X	X	X		X	X
CT (Chest, Abdomen, Pelvis) ⁱ	X								X	X ^d	Q 12 W
MRI Brain ⁱ	X										
Nivolumab infusion^j - ARM A		X			X	X	X	X			
Radiation Therapy^e - ARM B		X	X	X							
Endocrine Panels ^c	X				X	X	X	X			
Genomic Bloods/T-cell collection		X ^f				X ^f		X ^f			
Tumor biopsies	X ^g								X ^g		

a. Before each infusion.

b. SOC labs (COMP, CBC w/diff).

c. TSH, T3, T4

d. Scans day 63 ± 7.

e. Radiation is given to one, randomly selected lesion 30 Gy in 3 fractions of 10 Gy each (ARM B only)

f. to be collected PRIOR to infusion on days 1, 29 and 57.

g. Optional biopsy done at Day 63 (±7 days).

h. infusions will have a ± 3 day window.

i. prior scans will be valid until the screening period of 28 days

j. infusions will be ±24hrs from Day 1 of radiation. k. Patients will come off-study if they have disease progression. Patients will be followed for 30 days from the day they come off-study.

1.12 16.0 Study Procedures and Observations - Atezolizumab Alone and Atezolizumab plus Radiation

Procedure	Screening Visit (- 28 days)	Day 1 ^h	Day 3 ^h	Day 5 ^h	Day 22 ^h	Day 43 ^h	Day 64 ^h	Day 63 (+/-7days)	F/UQ 9wks (±7days) for first year ^k	Follow up Q12 weeks (±7days) after 1 st year ^k , years 2 and 3
Informed Consent	X									
Inclusion/Exclusion Criteria	X									
Medical History	X									
Pregnancy Test	X	X ^a			X ^a	X ^a	X ^a	X ^a		
Physical Examination Complete	X									
Physical Examination Limited		X			X	X	X	X	X	X
Vital Signs	X	X			X	X	X	X	X	X
Adverse Events Assessment	X	X			X	X	X	X	X	X
Serum Chemistry ^b	X	X			X	X	X	X	X	X
Hematology ^b	X	X			X	X	X	X	X	X
Urinalysis	X	X			X	X			X	X
CT imaging (Chest, Abdomen, Pelvis)	X							X	X ^d	Q 12 W
MRI Brain	X									
Atezolizumab/Pembrolizumab infusionⁱ - ARM A		X			X	X	X			

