- AEs should be followed to resolution or stabilization, and reported as SAEs if they become serious. This also applies to subjects experiencing AEs that cause interruption or discontinuation of immunotherapy, or those experiencing AEs that are present at the end of their participation in the study; such subjects should receive post-treatment follow-up as appropriate.
- All SAEs must be collected which occur within 30 days of discontinuation of dosing or completion of the patient's participation in the study if the last scheduled visit occurs at a later time. In addition, the Investigator should notify WCM of any SAE that may occur after this time period which they believe to be certainly, probably, or possibly related to immunotherapy.

1.16.1.8 21.8 Pregnancy

Sexually active women of childbearing potential must use an effective method of birth control during the course of the study, in a manner such that risk of failure is minimized.

Before enrolling women of childbearing potential (WOCBP) in this clinical trial, Investigators must review the guideline about study participation for WOCBP which can be found in the GCP Manual for Investigators. The topics include the following:

- General Information
- Informed Consent Form
- Pregnancy Prevention Information Sheet
- Drug Interactions with Hormonal Contraceptives
- Contraceptives in Current Use
- Guidelines for the Follow-up of a Reported Pregnancy

Prior to study enrollment, WOCBP must be advised of the importance of avoiding pregnancy during trial participation and the potential risk factors for an unintentional pregnancy. The subject must sign an informed consent form documenting this discussion.

All WOCBP MUST have a **negative** pregnancy test within 72 hours **prior** to receiving immunotherapy. The minimum sensitivity of the pregnancy test must be 25 IU/L or equivalent units of HCG. If the pregnancy test is positive, the subject must not receive nivolumab or atezolizumab and must not be enrolled in the study.

In addition, all WOCBP should be instructed to contact the Investigator immediately if they suspect they might be pregnant (e.g., missed or late menstrual period) at any time during study participation.

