If following initiation of study treatment, it is subsequently discovered that a trial subject is pregnant or may have been pregnant at the time of immunotherapy exposure, including during at least 6 half-lives after product administration, the immunotherapy will be permanently discontinued in an appropriate manner (e.g., dose tapering if necessary for subject safety). Exceptions to immunotherapy discontinuation may be considered for life-threatening conditions only after consultation with the Principal Investigator or as otherwise specified in this protocol. Protocol-required procedures for study discontinuation and follow-up must be performed on the subject unless contraindicated by pregnancy (e.g., x-ray studies). Other appropriate pregnancy follow-up procedures should be considered if indicated. In addition, the course of the pregnancy, including perinatal and neonatal outcome. Infants should be followed for a minimum of eight weeks.

1.17 22.0 Registration Procedures

1.17.1.1 22.1 Patient Registration

Patients will be centrally registered with the Office of Billing Compliance. To register a patient, submit the following documents via the JIRA Registration Process:

- Legible copy of the HRBAF
- First and last page of signed informed consent form

Registration must be completed within 24 hours of the signing of informed consent.

1.17.1.2 22.2 Administrative Section

1.17.1.2.1 22.2.1 Compliance with the Protocol and Protocol Revisions

The study will be conducted as described in the final approved protocol. Documentation of approval signed by the chairperson or designee of the IRB(s) will be sent to the WCM protocol manager.

All revisions (protocol amendments, administrative letters, and changes to the informed consent) will be submitted to the WCM protocol manager. The Investigator will not implement any deviation or change to the protocol without prior review and documented approval/favorable opinion from the IRB of an Amendment, except where necessary to eliminate an immediate hazard(s) to study patients.

1.17.1.2.2 22.2.2 Informed Consent

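### The eligibility criteria require less post-dose contraception than the 5 months that the protocol's own drug-safety sections tell sites to advise

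*Combined protocol and SAP*

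**What the plan says.** Two eligibility items set a contraception period that extends past treatment.

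- Section 8.1, inclusion 12: a woman of childbearing potential "must be using an adequate method of contraception to avoid pregnancy throughout the study and for up to 8 weeks after the study".
- Section 8.2, exclusion 10a: a woman is excluded if she cannot or will not avoid pregnancy "for the entire study period and for at least 8 weeks after cessation of study drug".

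The drug-safety sections use a longer period, both on grounds of fetal harm.

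- Section 3.6.10 (nivolumab) tells sites to advise contraception during treatment and "for at least 5 months after the last dose of nivolumab".
- Section 4.5.7 (atezolizumab) tells sites to advise women to "use effective contraception during treatment with Atezolizumab and for at least 5 months after the last dose".

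Section 21.8 has its own rule: "Sexually active women of childbearing potential must use an effective method of birth control during the course of the study". It gives no period after the last dose. It also requires counselling before enrolment: "The subject must sign an informed consent form documenting this discussion". The documents give no contraception period for pembrolizumab, which is allowed in the urothelial cohort.

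**The concern.** The protocol states a safety minimum as advice, then sets a shorter one as the condition of entry. A woman prepared to use contraception for only 8 weeks after her last dose is not excluded by 10a, although sites are told to advise 5 months.

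Item 12 has two further faults. Its *up to* is a ceiling where the purpose calls for a floor. It also counts from the end of the study, while the risk described in Sections 3.6.10 and 4.5.7 follows the last dose. The two items therefore differ in direction and starting point as well as falling short of the advice.

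What is at stake is fetal exposure in the months after treatment. The trial's endpoint, randomisation, analysis and sample size are unaffected.

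**Working it through.** The plan gives no figure to reproduce, so the check compares the texts and converts units.

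**Inputs from the documents**

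- Advised period: at least 5 months after the last dose (Sections 3.6.10 and 4.5.7). 5 × 30.44 = 152 days; by calendar months, 150 to 153.
- Exclusion 10a: at least 8 weeks after study drug stops, 8 × 7 = 56 days, plus the whole study period.
- Inclusion 12: the whole study period, plus up to 56 days after it.
- Dosing interval: 14 days for nivolumab, 21 days for atezolizumab.
- Off-study follow-up (footnote k, Sections 15.0 and 16.0): "Patients will be followed for 30 days from the day they come off-study".

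**Assumed quantities**

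- D: days from the last dose to the end of the study for that patient. The documents point both ways. Footnote k takes patients off study at progression and follows them for 30 days, and Section 17.2 has a similar limit after withdrawal. The Protocol Summary, however, gives follow-up of up to 3 years, and Section 29.1 follows all patients for survival.
- w: days that item 12 actually requires after the study, from 0 (*up to* read as a pure ceiling) to 56 (credited in full).

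**Formula.** Both items must be met, so the days required after the last dose are max(56, D + w). The shortfall is max(0, 152 − max(56, D + w)).

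| D (days) | Situation | Shortfall, w = 56 | Shortfall, w = 0 |
|---|---|---|---|
| 0 | study ends at last dose | 152 − 56 = 96 | 96 |
| 30 | off study at last dose, then 30 days | 152 − 86 = 66 | 96 |
| 30 + 14 = 44 | last dose one 2-week interval earlier | 152 − 100 = 52 | 96 |
| 30 + 21 = 51 | last dose one 3-week interval earlier | 152 − 107 = 45 | 96 |
| 56 | longer study period | 152 − 112 = 40 | 96 |
| 96 | longer study period | 152 − 152 = 0 | 152 − 96 = 56 |
| 152 | longer study period | 0 | 0 |

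The upper bound is 96 days under either reading (94 to 97 by calendar months), because 10a guarantees 56 days from the last dose. If the study ends after the 30-day follow-up, and the last dose was no more than one interval before coming off study, crediting item 12 in full leaves 52 to 66 days (2-week dosing) or 45 to 66 days (3-week dosing).

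**Does Section 21.8 close the gap?** Not in the visible text. Its birth-control rule ends with the study. Its other time window, "including during at least 6 half-lives after product administration", concerns what to do when a pregnancy is found after exposure; it sets no contraception period.

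**The case against.** The strongest reply is that nothing here is contradictory. Exclusion 10a is a floor, so a site can apply it and still advise 5 months. The drug-safety sections are part of the protocol, and Section 22.2.1 says the study is run as the protocol describes. An entry criterion records willingness on one day and cannot control behaviour months later; that is the job of counselling and consent, which Section 21.8 requires. That section also sends investigators to guidance for women of childbearing potential that includes a pregnancy-prevention sheet. The 5 months may reach patients that way. The size is uncertain too: if the study period includes survival follow-up, or doses were withheld for some time before a patient came off study, D is larger and the shortfall may vanish. Few women may be affected.

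Much of this stands. The texts do not force a choice, the consent and guidance documents cannot be seen, and the shortfall depends on D and w. Counting from the study's end cannot by itself shorten cover, since D only adds days. None of it removes the mismatch: the visible requirements accept a commitment shorter than the advised minimum, and a fetal-safety period should not depend on an undefined end of study.

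A narrower objection is that the correction could shorten the period for women followed long after their last dose. With the study-period wording kept, the corrected requirement is the longer of D and 152 days. Compared with item 12 credited in full (D + 56), that is shorter once D exceeds 96, by at most 56 days, but it never falls below 5 months.

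**Conclusion.** The point holds. The mismatch between the criteria and the drug-safety sections is certain from the text; its practical size is not. For nivolumab and atezolizumab the shortfall lies between 0 and about 96 days, depending on when the study is taken to end and how *up to* is read.

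The number of women concerned is unknown. It may be small if this trial resembles the two reference trials in Sections 3.4 and 4.3 (median ages 62 and 66; 75% and 78% male), which is an assumption. What women are actually told cannot be judged without the consent text. The point should be fixed because the potential harm is serious and the criteria set the wrong duration as written.

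**What to change.** In inclusion 12, exclusion 10a and Section 21.8, require effective contraception during treatment and for at least 5 months after the last dose of nivolumab or atezolizumab, keeping the existing requirement for the study period. In item 12, change *up to* to *at least*, and count from the last dose instead of the study.

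For pembrolizumab, the sponsor should insert the period from that drug's own safety information, since the documents support no figure. Check that the consent form and other patient-facing text agree; this also reaches women already enrolled, whom a change in eligibility wording cannot.

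The cost is amendment wording in three places and a consent check. No procedures are added, and the sample size and analysis do not change.

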9.0 Study Therapy [Nivolumab]

9.1 Nivolumab

Nivolumab is a human monoclonal antibody that blocks the interaction between PD-1 and its ligands, PD-L1 and PD-L2. Nivolumab is an IgG4 kappa immunoglobulin that has a calculated molecular mass of 146 kDa. Binding of the PD-1 ligands, PD-L1 and PD-L2, to the PD-1 receptor found on T cells, inhibits T-cell proliferation and cytokine production. Upregulation of PD-1 ligands occurs in some tumors and signaling through this pathway can contribute to inhibition of active T-cell immune surveillance of tumors. Nivolumab is a human immunoglobulin G4 (IgG4) monoclonal antibody that binds to the PD-1 receptor and blocks its interaction with PD-L1 and PD-L2, releasing PD-1 pathway-mediated inhibition of the immune response, including the anti-tumor immune response. In syngeneic mouse tumor models, blocking PD-1 activity resulted in decreased tumor growth.

Patients with Renal cell carcinoma will receive Nivolumab intravenously at a flat dose of 240mg every two weeks. Infusions will be given over 60 minutes (not bolus or IV push).

In Arm A:

Patient with Renal Cell carcinoma will receive nivolumab alone Days* 1, 15, 29, 43 and 57.

(* - infusions will have a \pm 3 days window to accommodate inevitable scheduling changes and holidays)

In Arm B:

Radiation is given to one lesion, 30 Gy in 3 fractions of 10 Gy each, over one week interval (with a minimum of 36 hours between each fraction), conformally or by intensity modulated radiation treatment to maximally spare normal tissue.

On the day of radiation (Day 1) immunotherapy is administered and repeated on the scheduled days. Patients will receive radiation on Day 1 and immunotherapy will be given \pm 24hr from Day 1.

Patients on both treatment arms will undergo re-imaging on Day 63 (\pm 7 days) (after the first 5 doses of Nivolumab) and every 9 (\pm 7 days) weeks for one year and every 12 weeks (\pm 7 days) thereafter. The first dose will be administered on Day 1 (\pm 24hrs) and repeated on Days 15, 22, 43 and 57. Radiation will be delivered every other day (with a minimum of 36 hours between the fractions) preferably starting on a Monday. A dose of 10 Gy x 3 days will be tested.

9.2 Preparation and Administration of Nivolumab

Dose Calculations

For Advanced Renal cell carcinoma: Nivolumab is given every 2 weeks. The recommended dose of nivolumab is a flat dose of 240mg administered as an intravenous infusion over 60 minutes every 2 weeks until disease progression or unacceptable toxicity.

Visually inspect drug product solution for particulate matter and discoloration prior to administration. Nivolumab is a clear to opalescent, colorless to pale-yellow solution. Discard the vial if the solution is cloudy, discolored, or contains extraneous particulate matter other than a few translucent-to-white, proteinaceous particles. Do not shake the vial.

9.2.1 Preparation

1. Withdraw the required volume of nivolumab and transfer into an intravenous container.
2. Dilute nivolumab with either 0.9% Sodium Chloride Injection, USP or 5% Dextrose Injection, USP to prepare an infusion with a final concentration ranging from 1 mg/mL to 10 mg/mL.
 - Mix diluted solution by gentle inversion. Do not shake.
 - Discard partially used vials or empty vials of nivolumab.

9.2.2 Storage of Infusion

The product does not contain a preservative. After preparation, store the nivolumab infusion either:

- At room temperature for no more than 4 hours from the time of preparation. This includes room temperature storage of the infusion in the IV container and time for administration of the infusion or
- Under refrigeration at 2°C to 8°C (36°F to 46°F) for no more than 24 hours from the time of infusion preparation.

Do not freeze.

